4.7 Adverse events

[figure not shown]
As one would expect, most adverse events are related to the medical grade adhesives used to secure the sensor for 14 days. Sensor-wear-related symptoms were recorded as adverse events in the IMPACT trial if the effects were severe and lasted for >7 days, or if the patient required prescription medication for the event to resolve (15). Adverse event severities were recorded on the basis of a health-care professional's assessment of mild, moderate, or severe events. IMPACT reported 13 cutaneous adverse events in 10 patients, and were categorised as mild (three cases), moderate (four cases), and severe (six cases). Seven participants withdrew from the study due to device-related adverse events or repetitive occurrences of sensor insertion-related symptoms. For participants with adverse events involving skin symptoms during this trial, symptoms (including severe) were resolved by use of barrier products (eg, Cavilon spray) or drug therapy (eg, zinc ointment, Fenistil gel, or hydrocortisone cream) as prescribed, or simply by relocating the device to another area of the skin such that the effects were maintained at a tolerable, background level (28). In other cases, although the adverse events were generally mild or moderate, the longevity of the symptoms, despite use of treatment, contributed to the participant's decision to withdraw from the trial. Investigations have since identified isobornyl acrylate as the likely agent causing contact dermatitis (29)

Since completion of the IMPACT trial, minor design changes have been made to FSL. These changes are expected to improve breathability of the skin that is in contact with the sensor and to facilitate the exclusion of moisture between the sensor–skin interface (28). During the children's study, five device related adverse events were reported in five (6%) participants, aged 6, 9, 10, 12 and 15 years: allergic reaction, blister, pink mark/scabbing and abrasion on sensor removal (n=2). Four were mild, one was moderate, all were resolved at study completion.(26)

4.8 FreeStyle Libre 2 flash-glucose monitoring system to be used in the present study

Flash-glucose monitoring system will consist of a body worn disc (about the size of £2 coin and) a hand held reader or a smart mobile phone with an app for flash glucose monitoring (Figure 1). Reader can display current glucose level as well as direction of glucose change and last 8 hours of glucose data. In contrast to the first generation FreeStyle Libre device, Libre 2 has the additional functionality of optional alarms, vibratory alerts or both when glucose levels become low and high. The “low glucose value” is factory set at 3.9 mmol/L and the “high glucose value” at 13.3 mmol/L. Users can adjust these values within a permitted range so they are tailored to their Type 1 diabetes management requirements.

Figure 1: FreeStyle Libre 2 flash glucose monitoring system (Abbott Diabetes Care, Oxon, UK):

4.9 Rationale for the Current Study

Use of FSL device in people with well controlled T1D has shown reduction in hypoglycemia burden. However, to date no randomised study with FSL2 has been undertaken in people with T1D and high HbA1c. Without randomised study evidence, there is a reluctance of payers to fund this device to wider group of T1D, potentially restricting its use in large number of people who could benefit. The purpose of this study is to determine whether use of flash glucose monitoring with FSL2 device will

improve HbA1c over a 24-week randomised period compared to self-monitoring of blood glucose in adults with sub-optimally controlled type 1 diabetes.

4.9.1 COVID-19 Pandemic: Supporting flexible visit schedules for vulnerable participants

In March 2020 the Covid-19 pandemic led to the suspension of research activity in the UK. In light of the ongoing and future risks and challenges Covid-19 presents, in May 2020 we updated our protocol to facilitate social distancing and protection of the people with diabetes who remain eligible and would like to participate in this trial. People with diabetes are categorised as 'vulnerable' due to the greater risks of adverse outcomes if they contract Covid-19. As such we have integrated flexibility to how sites and participants choose to progress through the schedule of assessments given the unknowns around Covid-19 transmission across England during 2020 / 2021. As is increasingly being adopted for routine diabetic clinics, participants will be able to join the trial through virtual consultation supported by video conferencing and telephone (when appropriate) or if available at individual sites through face to face clinics or a mixture of both. For those who choose to enter the trial by virtual means, any required devices, study documents and kits for HbA1c collections will be provided to participants free of charge with pre-paid return postage.

5 Objectives

The study's primary objective is to compare flash glucose monitoring with Freestyle Libre 2 (FSL2) device with self-monitoring of blood glucose over 24 weeks in adults & adolescents (16 years or older) with sub-optimally controlled (HbA1c 7.5% to 11%) type 1 diabetes.

5.1 Clinical Efficacy

The objective is to assess the clinical efficacy of flash glucose monitoring with FSL2 device relative to that with self-monitoring of blood glucose on glycated haemoglobin A1c (HbA1c) (primary clinical objective) and sensor-based glucose metrics (secondary clinical objectives; e.g. time spent in target glucose range 3.9 to 10 mmol/L).

5.2 Psychosocial efficacy

Evaluation of participants' responses in terms of quality of life, diabetes related distress, diabetes treatment satisfaction, low mood, needle burden and disordered eating behaviours will be assessed using validated questionnaires.

5.3 Cost-effectiveness

The objective is to assess the relative cost-effectiveness of the FSL2 device compared with self-monitoring in adults and adolescents with sub-optimally controlled type 1 diabetes, from the perspective of NHS England

5.4 Safety

The objective is to evaluate time spent in hypoglycaemia (sensor glucose levels < 3.0 mmol/l and other sensor based biochemical hypoglycaemia) and number of episodes of severe hypoglycaemia with FSL2 and self-monitoring of blood glucose

5.5 Process Evaluation (Utility & Acceptability)

The objectives are to explore the frequency and patterns of daily scans, duration of use of FSL2 device and explore participants' expectations and experiences

6 Study Design

An open-label, multi-centre, randomised, parallel study, in adults and adolescents (16 years and older) with type 1 diabetes and sub-optimal glycaemic control (HbA1c 7.5% to 11%), either on insulin pump treatment or multiple daily injections, contrasting flash glucose monitoring using FreeStyle Libre 2 device with traditional finger-stick glucose monitoring for 24 weeks. The study flow chart is outlined in Figure 2.

7 Study Participants

7.1 Study Population

This is a UK multi-centre and recruitment will take place at the following centres:

[figure not shown]
1. Diabetes Centres within Manchester University NHS Foundation Trust
2. Diabetes Centres within University Hospitals of Derby and Burton NHS Foundation Trust
3. University Hospitals Birmingham NHS Foundation Trust, Birmingham
4. Addenbrookes Hospital, Cambridge
5. Norfolk and Norwich University Hospital, Norwich
6. Queen Alexandra Hospital, Portsmouth
7. Ipswich Hospital, East Suffolk and North Essex NHS Foundation Trust, Ipswich

8. Wareham Surgery (Wareham) and The Adam Practice (Poole), NHS England Primary Care GP Practices

Each centre will aim to recruit between 25 to 30 participants up to a total of 180 participants. Additional diabetes centres surrounding above hospitals may act as participant identification centres. In addition, the study may be advertised via social media and other local media so people who don't usually attend above diabetes centres could also join the study providing unique opportunity for a wider group of people with sub-optimally controlled type 1 diabetes to join the study. If participants are outside the catchment area of the clinic, we will contact the clinical team responsible for the participant to confirm type 1 diabetes status and any other contraindications for study participation.

Potential participants will be identified by their treating clinicians and invited to contact the research team. They will be sent the study information leaflets and an invitation by post or in-person to join the study by the research team at least one day before the recruitment visit. The study may also be advertised via social media or posters displayed in clinic. Additionally, the study will be advertised in GP practices. . This will facilitate self-referral from interested candidates for screening purposes and optimise trial recruitment across centres.

Figure 2. Study flow chart

7.2 Inclusion Criteria

1. The participant is ≥ 16 years old
2. The participant has type 1 diabetes, as defined by WHO for at least 1 year or is confirmed C-peptide negative if duration of diabetes is < 1 years
3. Participant is treated with insulin pump or multiple daily injection for at least 12 weeks and no plans to change treatment modality during next 28 weeks
4. The participant is literate in English for safe study conduct
5. Screening HbA1c $\geq 7.5\%$ (58.5mmol/mol) and $\leq 11\%$ (97 mmol/mol) based on analysis from local, central or third party external laboratory

6. The participant is willing to wear study glucose sensor and scan for glucose levels at frequent intervals
7. The participant is willing to follow study specific instructions to improve glucose control
8. Female participants of child bearing age should be on effective contraception or not sexually active/no plans for pregnancy in the next 8 months.
9. The participant adopting a virtual pathway through the trial is able and willing to post study devices, questionnaires and blood collection kits back to the research team or to the laboratory using pre-paid postal services
10. The participant adopting a virtual pathway through the trial has internet connection, appropriate videoconferencing software and supporting devices to undertake video consultations where necessary.

7.3 Exclusion Criteria

1. Non-type 1 diabetes mellitus including those secondary to chronic disease
2. Any other physical disease or people with known severe mental illness (psychotic disorder, bipolar disorder, dementia, substance and alcohol dependence, learning disabilities, depression with active suicidal ideation) which are likely to interfere with the normal conduct of the study and interpretation of the study results as judged by the investigator
3. Current users of real-time glucose monitoring sensors or flash-glucose monitoring for more than 4 weeks within last 12 weeks
4. Initiation of medications/treatments known to interfere with glucose metabolism (e.g: metformin, SGLT2 inhibitors, GLP-1 agonists, Pramlintide) within the last 6 weeks or planning to start these medications within the next 6 months (patients on stable treatment is not an exclusion) or current or planned glucocorticoid use other than inhaled/ topical use.
5. Known or suspected allergy against insulin
6. Severe visual impairment
7. Complete loss of hypoglycaemia awareness
8. Patient receiving dialysis / pre-dialysis based on history
9. More than one episode of severe hypoglycaemia as defined by American Diabetes Association (30) in preceding 24 weeks as confirmed by clinical history or hospital notes; (severe hypoglycaemia is defined as an event requiring assistance of another person to actively administer carbohydrates, glucagon, or take other corrective actions including episodes of hypoglycaemia severe enough to cause unconsciousness, seizures or attendance

at hospital; children: severe hypoglycaemia is defined as an event associated with a seizure or loss of consciousness);

10. Total daily insulin dose ≥ 2 IU/kg/day
11. Pregnancy, planned pregnancy in the next 8 months, or breast feeding
12. Participant is using implanted internal pace-maker
13. Participants with medically documented allergy towards the adhesive (glue) of plasters or participant is unable to tolerate tape adhesive around sensor placement area
14. Serious skin diseases (e.g. psoriasis vulgaris, bacterial skin diseases) located at places of the body, which potentially are possible to be used for localisation of the glucose sensor)
15. Participant is currently abusing illicit drugs as judged by the investigator
16. Participant is currently abusing prescription drugs as judged by the investigator
17. Participant is currently abusing alcohol as judged by the investigator
18. Participant has elective surgery planned that requires general anaesthesia during the course of the study
19. Participant has a sickle cell disease, haemoglobinopathy; or has received or plan to receive red blood cell transfusion or erythropoietin within 12 weeks prior to time of screening or during study duration

8 Methods under Investigation

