Three years ago, in 2014 a new category of device was born: the FreeStyle Libre Flash Glucose Monitoring System (FSL) (Abbott Diabetes Care, Oxon, UK). This device is different to earlier CGM systems. Although it does produce real-time on-demand continuous glucose data, it does not alarm to alert users of rising or falling glucose levels. Hence the label: 'flash glucose monitoring'. The FSL device is a replaceable white disc, worn on the arm for 14 days. The sensor utilises wired enzyme technology (14) (osmium mediator and glucose oxidase enzyme co-immobilised on electrochemical sensor) to continuously measure interstitial glucose levels. It is factory calibrated and does not need calibration during use. Abbott provided potential users with the option of direct on-line purchase of FSL, without prior approval from health care providers. The Freestyle Libre (FSL) flash glucose monitor became available on prescription (subject to local health authority approval) in all four nations of the United Kingdom from November 2017, a watershed moment in the history of diabetes care. Freestyle Libre 2 (which is CE marked) has been produced by the manufacturer. This is identical to FSL but with the optional additional functionality of alarm alerts for users who fall outside of adequately controlled glucose levels. This model has yet to be assigned an official release date for the United Kingdom.

4.3 Evidence from randomised controlled trials:

The largest study to evaluate FSL is the IMPACT randomised controlled multicentre European trial (15). This study included 328 participants with well controlled ($\text{HbA1c} \leq 7.5\%, 59 \text{ mmol/mol}$) Type 1 diabetes, a third of which used CSII therapy. FSL use was associated with improvement in a range of glucose related outcomes: a 38% reduction in time spent in hypoglycaemia ($<3.9 \text{ mmol/l}$) with no change in total daily insulin dose. The reduction in hypoglycaemia was achieved within 2 weeks, despite no training on glucose data interpretation and no health care professional contact during this initial period, suggesting that users intuitively understood how to react to the data (Figure 1). There was an increase in glucose time in range combined with a reduction in glycaemic variability. The HbA1c was unchanged.

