9.4.1 Randomisation scheme

Randomisation to one of the two intervention arms (24-weeks use of flash-glucose monitoring or 24 weeks use of conventional finger-stick glucose monitoring) will use the minimisation method, with a random element to improve allocation concealment. We will minimise over the following factors: study centre (Birmingham; Cambridge; Derby; Manchester; Norwich; Portsmouth), baseline HbA1c (7.5%-9.0%; >9.0%-11%), treatment modality (Multiple daily injections (MDI); Continuous Subcutaneous insulin Infusion (CSII)), prior participation in structured education course (yes; no) and current use of bolus calculator (yes; no).

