#### **5.2.3 Sensitivity analyses**

Sensitivity analyses will examine robustness of the primary outcome results to assumptions regarding missing data by performing multiple imputation (see Section 5.3).

The primary outcome analysis will also be repeated having included additional covariates for the consideration of improved precision. These covariates will include age, sex, BMI duration of diabetes, deprivation index quintile.

Complier-Adjusted Causal Effect (CACE) will be used, implemented using an instrumental variables approach, to estimate the causal effect of the FSL device glucose monitoring relative to finger-stick glucose monitoring. Appropriate definitions of non-compliance (adherence) will be investigated within this sensitivity analysis, including the simple definition in the finger-stick monitoring arm of non-compliance equating to use of FSL device glucose monitoring for at least 10 days between the 3-month and 6-month outcome assessment.

Additional sensitivity analyses will be conducted to assess the impact of primary outcome data collected outside the visit window as specified in the protocol, that is:

- +/- 2 weeks of the planned visit date or
- +/- 4 weeks of the planned visit date.

Further sensitivity analyses will be performed to assess the potential impact of COVID-19 on the primary outcome. These will include the exclusion of participants whose treatment or outcome assessment was deemed severely impacted by COVID-19.

Finally, additional sensitivity analyses will be introduced to examine for the impact of protocol deviations or other unexpected events that may not have been captured in the protocol, including the impact on key secondary outcomes, where deemed necessary.

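### Exclusion 3 does not exclude short-term current flash users or people planning to get flash or real-time CGM, so control-arm use could dilute the primary comparison

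*Protocol*

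**What the plan says.** **Eligibility.** Protocol 7.3, exclusion 3, and the same item in the synopsis bar "Current users of real-time glucose monitoring sensors or flash-glucose monitoring for more than 4 weeks within last 12 weeks". There is no clause on planned use.

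**Other forward-looking criteria.** Inclusion 3 (Protocol 7.2) requires "no plans to change treatment modality during next 28 weeks", but Protocol 9.4.1 defines treatment modality as injections or pump, so it does not cover glucose monitoring. Exclusion 4 covers glucose-active drugs started recently "or planning to start these medications within the next 6 months". Other criteria look ahead for pregnancy (8 months), elective surgery under general anaesthesia, and transfusion or erythropoietin.

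**Access outside the trial.** Protocol 4.2 says that first-generation FreeStyle Libre (FSL) "became available on prescription (subject to local health authority approval) in all four nations of the United Kingdom from November 2017" and that "Abbott provided potential users with the option of direct on-line purchase of FSL, without prior approval from health care providers". It describes FSL2 as the same product with optional alarms added.

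**Control arm.** Protocol 13.2 says that controls use their usual finger-stick meter throughout. Protocol 9.4.4 says that pre-study diabetes treatment continues unchanged.

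**Analysis.** The primary analysis is an intention-to-treat ANCOVA (Protocol 14.2 and 14.2.1; SAP 3.3 and 5.2.1). SAP 5.2.3 adds a complier-adjusted (CACE) sensitivity analysis. One candidate definition of control-arm non-compliance there is "use of FSL device glucose monitoring for at least 10 days between the 3-month and 6-month outcome assessment". The sample size (Protocol 14.1) has no allowance for crossover.

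**The concern.** The trial compares flash monitoring with finger-stick testing, so the co-intervention that matters most is flash or CGM obtained outside the trial. The criteria look ahead for several lesser disturbances of HbA1c but not for this one.

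Two kinds of people pass exclusion 3: someone who began wearing a flash sensor a few weeks before screening, and someone who has applied for a sensor or means to buy one. They are plausibly the likeliest to use a sensor if allocated to finger-stick testing. Under intention to treat they stay in the control arm, and any HbA1c benefit they gain is subtracted from the treatment difference. The CACE analysis may describe this afterwards, but it does not change who is randomised or restore the power of the primary comparison.

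**Working it through.** **Step 1: who passes exclusion 3.**
- *Flash user at screening, 4 weeks or less in the last 12:* not excluded. No other criterion in 7.2 or 7.3 addresses this.
- *Real-time CGM user at screening, 4 weeks or less:* depends on the reading. If the 4-week limit qualifies both devices, this person passes. If it qualifies flash only, every current CGM user is barred.
- *Person planning to obtain flash or CGM:* not excluded on either reading.

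**Step 2: reproduce the plan's figures.** Inputs from Protocol 14.1: difference 0.4%, SD 0.8%, 64 evaluable per arm, two-sided 5%.
- t-test: standard error = 0.8 × √(2/64) = 0.1414; noncentrality = 0.4 / 0.1414 = 2.83; 126 df; power 80.1%. Stated: 80%.
- ANCOVA with baseline correlation 0.5: residual SD = 0.8 × √(1 − 0.5²) = 0.693; standard error = 0.693 × √(2/64) = 0.1225; noncentrality = 0.4 / 0.1225 = 3.27; 125 df; power 90.0%. Stated: 90%.

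Both agree with the plan.

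**Step 3: dilution.** Let c be the share of controls who gain the full flash effect. The control mean then improves by 0.4c, so the intention-to-treat difference is 0.4 − 0.4c = 0.4(1 − c). The SD is held fixed. The documents give no value for c, so a range is shown.

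| c (assumed) | Difference | t-test power, SD 0.8 | ANCOVA power, correlation 0.5, SD 0.8 | ANCOVA power, correlation 0.5, SD 0.9 |
|---|---|---|---|---|
| 0 | 0.40% | 80.1% | 90.0% | 82.1% |
| 5% | 0.38% | 76.0% | 86.8% | 78.1% |
| 10% | 0.36% | 71.4% | 83.1% | 73.7% |
| 15% | 0.34% | 66.5% | 78.7% | 68.7% |
| 20% | 0.32% | 61.2% | 73.7% | 63.5% |

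The last column is included because Protocol 14.1 says that the SD may lie between 0.8 and 0.9.

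**Step 4: what the rows measure.** They describe all control crossover. A change to eligibility can prevent only the part that is already current or intended at screening, so each loss is an upper limit on what the fix recovers.

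**The case against.** The strongest reply is that the protocol should be read as a whole. Controls are described as using finger-stick meters throughout (13.2), inclusion 7 requires willingness to follow study instructions, and significant non-adherence is a withdrawal criterion (9.9). Most of the participant leaflets was removed before review, and they may tell controls not to use personal sensors. A reader therefore cannot infer that the plan permits sensor use in the control arm. What remains is narrower: none of these provisions asks about current or planned sensor use before randomisation, and a leaflet instruction would not change who is eligible.

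Four stronger readings are tempting and are not supported.
- *Someone who wore a sensor for 11 of the last 12 weeks and has just stopped can enter.* This leans on the word "current". The natural reading of the 12-week window is cumulative exposure, which excludes that person.
- *Controls can obtain the trial device itself.* Protocol 4.2 says that FSL2 had no UK release date. The likely contaminants are first-generation FSL, on prescription only with local approval or by self-purchase, or real-time CGM.
- *The SAP expects controls to use FSL.* SAP 5.2.3 only lists such use among definitions to be investigated. It is a contingency.
- *5% crossover breaks the 80% power target.* That holds for the t-test, and for ANCOVA at SD 0.9. On the planned ANCOVA at SD 0.8, power is still 83% at 10% crossover and falls below 80% between 10 and 15%.

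Two further points stand. Dilution pulls towards no difference, so it would not by itself create a false benefit. Protocol 14.1 also considered effects of 0.43% to 0.7% plausible; at 0.43%, 7% full crossover leaves 0.43 × 0.93 = 0.40%.

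**Conclusion.** The eligibility gap is real and the direction of its effect is clear. Exclusion 3 limits past use only, no other criterion covers current short-term use or planned use, and the primary analysis keeps control users in the control arm.

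The size is unknown. If c is 5 to 20%, ANCOVA power at correlation 0.5 and SD 0.8 falls from 90% to between 87% and 74%, and the expected difference falls from 0.40% to between 0.38% and 0.32%. This rests on an assumed c, on each crossover giving the full effect, and on an unchanged SD; partial or late use would dilute less. The point is a worthwhile, inexpensive improvement to the eligibility wording. It does not show that the trial is underpowered.

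**What to change.** Reword exclusion 3 in Protocol 7.3 and in the synopsis so that it excludes flash or real-time CGM use in any of three forms:
1. in use at screening;
2. more than 4 weeks in total over the preceding 12, whether or not since stopped;
3. planned outside the trial, prescribed or self-funded, during the following 28 weeks.

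The 28 weeks match inclusion 3 and cover the planned 26 to 27 weeks from Visit 1 (2 to 3 weeks before randomisation) to Visit 7 (24 weeks after). Ask the question at Visit 1 and reconfirm it at Visit 3 before randomisation.

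**Cost.** Amended wording and one screening question. A few otherwise eligible candidates would be turned away; the documents give no figure for how many. Stated intention cannot be verified, and crossover decided after randomisation is not prevented. Recording personal flash or CGM use in both arms as a named deviation category, in place of the general "other" category in SAP 3.2.2, would at least make that remainder visible.
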